8.2.2 Definition of Serious Adverse Events (SAE)

Serious Adverse Events (SAE)

Adverse events are classified as serious or non-serious. A serious adverse event is any AE that, in the view of either the investigator or the sponsor, is:

- fatal
- life-threatening
- requires or prolongs hospital stay
- results in persistent or significant disability or incapacity
- a congenital anomaly or birth defect
- an important medical event when the event does not fit the other outcomes, but the event may jeopardize the patient and may require medical or surgical intervention (treatment) to prevent one of the other outcomes.
- required intervention to prevent permanent impairment or damage (for devices only)

Important medical events are those that may not be immediately life threatening but are clearly of major clinical significance. They may jeopardize the subject and may require intervention to prevent one of the other serious outcomes noted above. For example, drug overdose or abuse, a seizure that did not result in in-patient hospitalization, or intensive treatment of bronchospasm in an emergency department would typically be considered serious.

8.2.3 Classification of an Adverse Event

8.2.3.1 Severity of Event

For adverse events (AEs) not included in the protocol defined grading system, the following guidelines will be used to describe severity.

- Mild Events require minimal or no treatment and do not interfere with the participant's daily activities.
- Moderate Events result in a low level of inconvenience or concern with the therapeutic measures. Moderate events may cause some interference with functioning.

Severe – Events interrupt a participant's usual daily activity and may require systemic drug therapy or other treatment. Severe events are usually potentially life-threatening or incapacitating. Of note, the term "severe" does not necessarily equate to "serious"

8.2.3.2 Relationship to Study Intervention

All adverse events (AEs) must have their relationship to genetic counseling assessed by the clinician who examines and evaluates the participant based on temporal relationship and his/her clinical judgment. The degree of certainty about causality will be graded using the categories below. In a clinical trial, the study product must always be considered.

• Related – The AE is known to occur with the genetic counseling, there is a reasonable possibility that the genetic counseling caused the AE, or there is a temporal relationship between the genetic counseling and event. Reasonable possibility means that there is evidence to suggest a causal relationship between the genetic counseling and the AE.

Not Related – There is not a reasonable possibility that the administration of the genetic counseling caused the event, there is no temporal relationship between the genetic counseling and event onset, or an alternate etiology has been established

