2.3 Risk/Benefit Assessment

2.3.1 Known Potential Risks

This study provides genetic counseling and testing to all participants. The method of genetic counseling varies between randomization groups. There are no known risks that differ between forms of genetic counseling including web-based, telephone, or virtual visit methods. Potential risks of genetic counseling include anxiety, stress, or discomfort that can arise during genetic counseling. Genetic counseling during this study will be conducted by trained genetic counselors following clinical guidelines genetic counseling in PD. For participants randomized to IMAGINE-PD, participants will have access to a genetic counselor via email for any follow up or clarification questions. The risks of genetic testing are relevant to all participants, which include the potential for emotional, social, or financial consequences of the testing results. Some people may feel angry, sad, anxious, or guilty about the results. There is also a risk of genetic discrimination or of re-identification of deidentified genetic results.

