8.2.3.3 Expectedness

The PI will be responsible for determining whether an adverse event (AE) is expected or unexpected. An AE will be considered unexpected if the nature, severity, or frequency of the event is not consistent with the risk information previously described for genetic counseling.

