8.2.4 Time Period and Frequency for Event Assessment and Follow-Up

Safety will be assessed by monitoring and recording potential adverse effects using the CTCAE at each study visit. Participants will be monitored by study outcome measures. If CTCAE

Page 28 of 41

grading does not exist for an adverse event, the severity of mild, moderate, severe, life-threatening, and death, corresponding to Grades 1-5, will be used whenever possible.

At each contact with the subject, the investigator will seek information on adverse events by nondirective questioning and, as appropriate, by examination. Adverse events may also be detected when they are volunteered by the subject during the screening process or between visits, or through physical examination, laboratory test, or other assessments. Information on all adverse events will be recorded in the source documentation. To the extent possible, adverse events will be recorded as a diagnosis and symptoms used to make the diagnosis recorded within the diagnosis event.

As much as possible, each adverse event or follow-up information will be evaluated to determine:

- 1. Severity grade (CTCAE Grade 1-5)
- 2. Duration (start and end dates)
- 3. Relationship to the study treatment or process [Reasonable possibility that AE is related: No (unrelated/ not suspected) or Yes (a suspected adverse reaction)]. If yes (suspected) is the event possibly, probably or definitely related to the investigational treatment?
- 4. Expectedness to study treatment or process [Unexpected if the event severity and/or frequency is not described in the investigator brochure (if applicable) or protocol].
- 5. Action taken with respect to study or investigational treatment or process (none, dose adjusted, temporarily interrupted, permanently discontinued, unknown, not applicable)
- 6. Whether medication or therapy taken (no concomitant medication/non-drug therapy, concomitant medication/non-drug therapy)
- 7. Whether the event is serious

Once an adverse event is detected, it should be followed until its resolution or until it is judged to be permanent, and assessment should be made at each visit (or more frequently, if necessary) of any changes in severity, the suspected relationship to the study treatment, the interventions required to treat it, and the outcome.

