8.2.6 Serious Adverse Event Reporting

The study clinician will immediately report to the IRB any serious adverse event, whether or not considered genetic counseling related, including those listed in the protocol and must include an assessment of whether there is a reasonable possibility that genetic counseling caused the event.

New information regarding the SAE will be reported as it becomes available and in the same manner that the initial SAE (i.e. SAE form). All serious adverse events (SAEs) will be followed until satisfactory resolution or until the site investigator deems the event to be chronic or the participant is stable.

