8.2.7 Reporting Events to Participants

For all events, AE and SAE, participants will be informed via mailing at the end of the study. Any AE or SAE deemed study intervention related will be included in the informed consent for subsequent participants.

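### The causality, expectedness and SAE-statement rules refer to genetic counseling only, while Section 8.2.4 uses a wider reference and another scale, so harm from the test result can receive contradictory codes

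*Combined protocol and SAP*

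**What the plan says.** Section 2.3.1 deals with two kinds of risk in turn. Counseling may bring anxiety, stress or discomfort. It then turns to testing: "The risks of genetic testing are relevant to all participants, which include the potential for emotional, social, or financial consequences of the testing results". It adds genetic discrimination and re-identification. Genetic testing is Section 6.2, within Section 6 on the study intervention.

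The safety sections use these references:

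- **8.2.3.2, relatedness:** "All adverse events (AEs) must have their relationship to genetic counseling assessed by the clinician who examines and evaluates the participant". An event is Related if it is known to occur with counseling, if there is a reasonable possibility that counseling caused it, "or there is a temporal relationship between the genetic counseling and event". It is Not Related if there is no reasonable possibility, if there is no temporal relationship, "or an alternate etiology has been established".
- **8.2.3.3, expectedness:** the comparison is with the "risk information previously described for genetic counseling".
- **8.2.6, serious events:** the report must contain an "assessment of whether there is a reasonable possibility that genetic counseling caused the event".
- **8.2.4, per-event evaluation list:** the item is "Relationship to the study treatment or process". A suspected event is then graded possibly, probably or definitely related. Expectedness is judged against the protocol, or an investigator brochure if there is one.
- **8.2.7, consequence:** "Any AE or SAE deemed study intervention related will be included in the informed consent for subsequent participants".

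**The concern.** The protocol treats the test result as a source of harm in its own right, but the section that defines relatedness has no place for it. A clinician asked only whether counseling caused an event may reasonably answer that the result did, not the session. Section 8.2.4 asks a different question on a different scale, so the same event may be answered differently there.

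The code has uses. Section 8.2.7 makes relatedness the trigger for updating later consent forms. The causality statement in 8.2.6 is what the IRB reads beside each serious event. Section 9.4.4 plans no statistical analysis of safety endpoints, so counts of related events would be reported without any further analysis behind them. A loose definition therefore passes straight into the safety account of the trial.

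**Working it through.** No arithmetic decides this point. The check is to set the rules side by side and apply them to two kinds of event that Section 2.3.1 names.

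| Feature | 8.2.3.2 and 8.2.3.3 | 8.2.4 |
|---|---|---|
| Reference for causality | Counseling | Study treatment or process |
| Reference for expectedness | Counseling risk information | Protocol, or brochure if applicable |
| Scale | Related / Not Related | No, or Yes graded possibly / probably / definitely |
| Force | Mandatory | To be done as far as possible |
| Names the test result | No | No |

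**Event A: marked distress soon after a participant learns of carrier status.** Under Sections 4.1 and 6.2 the result is given by virtual visit or telephone with a genetic counselor, so the distress follows a counseling session.
1. The temporal limb of 8.2.3.2 is met, and it is sufficient alone: Related.
2. If the clinician regards the result as the established cause, the alternate-etiology limb is met. It too is joined by *or* and sufficient alone: Not Related.
3. No precedence rule exists, so both codes are permitted.
4. Under 8.2.4, disclosure of a result is readily part of the study process: related.

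**Event B: discrimination or a financial consequence of the result that surfaces months later.** Such an event can be recorded, because adverse events are collected until study completion (8.2.5) and reviewed up to Visit 4, Day 210-238 (12.1).
1. Section 8.2.3.2 sets no time window. A clinician may see no temporal or causal link to the session: Not Related.
2. Under 8.2.4 the event can be related to the study process.
3. Expectedness also splits. Section 2.3.1 lists discrimination among the testing risks, so it is outside the counseling reference of 8.2.3.3 (unexpected) but described in the protocol for 8.2.4 (expected).

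**The consent trigger.** Section 8.2.7 speaks of relation to the study intervention. The heading of 8.2.3.2 uses that term, but its text narrows it to counseling, whereas Section 6 includes testing. Whether a result-related event reaches the consent form depends on which meaning the reader takes.

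**Exposure.** All 320 planned participants are to receive a result. With the planned shares in Section 9.2, 320 × (0.45 + 0.10) = 176 would be variant carriers. Both figures count people who receive results, not miscoded events.

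**The case against.** The strongest reply is that this is loose drafting with little consequence. Much of that stands.

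- A reader might infer that causality is judged against counseling everywhere. It is not: 8.2.4 is wider and can cover the test and its result. But 8.2.4 does not override the mandatory wording of 8.2.3.2, and parts of it narrow again to the treatment alone. It adds a second answer instead of settling the first.
- A reader might infer that result-related harm would always be coded Not Related. That does not follow. Results are disclosed inside a counseling session, so early distress can meet the temporal limb. The code is undetermined, and the risk of Not Related is greater for late events.
- A reader might infer that such harm is kept from the IRB or from the unanticipated-problem route. The documents say otherwise. Section 8.2.6 sends every serious event to the IRB whatever its relatedness, and 8.3.1 judges unanticipated problems against participation in the research.
- The narrow expectedness rule would tend to class a result-related event as unexpected, which errs toward caution. That is fair, but it still contradicts 8.2.4.
- Other safeguards do not use the code. Test-related distress is a primary outcome through the IES-R, depression and anxiety are scored, and a concerning C-SSRS result triggers referral (9.4.4). These do not capture social or financial harm, and they do not correct a relatedness count.
- Section 2.3.1 already names these risks, and the consent form was not available for this review, so no claim can be made that it omits them.

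**Conclusion.** The point holds as an inconsistency. Three sections define relatedness, expectedness and the SAE causality statement against counseling alone. A fourth uses a wider reference and a different scale. None names the test result, which Section 2.3.1 lists as a risk for all participants. One event can be Not Related under 8.2.3.2 and related under 8.2.4, and can meet both categories within 8.2.3.2.

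The effect falls mainly on four things: non-serious adverse events, the causality statement that accompanies each serious event, counts of related events, and consent updates under 8.2.7. Its size in events cannot be stated, because the documents give no rate; Section 2.3.3 calls the risk of significant depression, anxiety or suicidality very low. The 176 planned carriers should not be read as a measure of effect, since nothing in the documents quantifies distress by carrier status.

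The conclusion assumes that clinicians apply 8.2.3.2 as worded and that no case report form instruction resolves the conflict. The forms are listed as an attachment (13.4) but were not available.

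**What to change.** 1. In 8.2.3.2, 8.2.3.3 and 8.2.6, replace *genetic counseling* with *genetic counseling, genetic testing or receipt of the genetic result*.
2. In 8.2.3.2, state that the study's own test result does not count as an alternate etiology.
3. Reconcile 8.2.3.2 with 8.2.4 so that one reference and one relatedness scale apply, with mutually exclusive categories. The study team should decide how timing and a true outside cause are weighed, and write that down. Bring 8.2.3.3 and 8.2.4 to one source for expectedness.

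There is no need to record which of the three elements is suspected. Result and counseling arrive together at the disclosure visit and often could not be separated.

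The cost is wording in four sections and a matching change to the adverse event form if it carries the present scale. No visit, procedure or sample size changes. The count of related events may rise slightly.

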8.2.3.3 Expectedness

The PI will be responsible for determining whether an adverse event (AE) is expected or unexpected. An AE will be considered unexpected if the nature, severity, or frequency of the event is not consistent with the risk information previously described for genetic counseling.

8.2.4 Time Period and Frequency for Event Assessment and Follow-Up

Safety will be assessed by monitoring and recording potential adverse effects using the CTCAE at each study visit. Participants will be monitored by study outcome measures. If CTCAE

Page 28 of 41

grading does not exist for an adverse event, the severity of mild, moderate, severe, life-threatening, and death, corresponding to Grades 1-5, will be used whenever possible.

At each contact with the subject, the investigator will seek information on adverse events by nondirective questioning and, as appropriate, by examination. Adverse events may also be detected when they are volunteered by the subject during the screening process or between visits, or through physical examination, laboratory test, or other assessments. Information on all adverse events will be recorded in the source documentation. To the extent possible, adverse events will be recorded as a diagnosis and symptoms used to make the diagnosis recorded within the diagnosis event.

As much as possible, each adverse event or follow-up information will be evaluated to determine:

- 1. Severity grade (CTCAE Grade 1-5)
- 2. Duration (start and end dates)
- 3. Relationship to the study treatment or process [Reasonable possibility that AE is related: No (unrelated/ not suspected) or Yes (a suspected adverse reaction)]. If yes (suspected) is the event possibly, probably or definitely related to the investigational treatment?
- 4. Expectedness to study treatment or process [Unexpected if the event severity and/or frequency is not described in the investigator brochure (if applicable) or protocol].
- 5. Action taken with respect to study or investigational treatment or process (none, dose adjusted, temporarily interrupted, permanently discontinued, unknown, not applicable)
- 6. Whether medication or therapy taken (no concomitant medication/non-drug therapy, concomitant medication/non-drug therapy)
- 7. Whether the event is serious

Once an adverse event is detected, it should be followed until its resolution or until it is judged to be permanent, and assessment should be made at each visit (or more frequently, if necessary) of any changes in severity, the suspected relationship to the study treatment, the interventions required to treat it, and the outcome.

8.2.5 Adverse Event Reporting

Reporting Period

Adverse events will be reported from the time of informed consent until study completion.

Protocol 843748–	
GET VIRTUAL PD	
IMAGINE-PD	Page 29 of 41

The investigator will report AEs and SAEs to the IRB/EC of record and other local regulatory groups per the local requirements.

8.2.6 Serious Adverse Event Reporting

The study clinician will immediately report to the IRB any serious adverse event, whether or not considered genetic counseling related, including those listed in the protocol and must include an assessment of whether there is a reasonable possibility that genetic counseling caused the event.

New information regarding the SAE will be reported as it becomes available and in the same manner that the initial SAE (i.e. SAE form). All serious adverse events (SAEs) will be followed until satisfactory resolution or until the site investigator deems the event to be chronic or the participant is stable.

8.2.7 Reporting Events to Participants

For all events, AE and SAE, participants will be informed via mailing at the end of the study. Any AE or SAE deemed study intervention related will be included in the informed consent for subsequent participants.

8.2.8 Reporting of Pregnancy

Pregnancy, in and of itself, is not regarded as an AE. Genetic counseling may have different implications for pregnancy women, we exclude pregnant women at study enrollment, however, would not exclude pregnant women from subsequent study visits at the discretion of the study participant.

8.3 Unanticipated Problems

8.3.1 Definition of Unanticipated Problems (UP)

The Office for Human Research Protections (OHRP) considers unanticipated problems involving risks to participants or others to include, in general, any incident, experience, or outcome that meets all the following criteria:

- Unexpected in terms of nature, severity, or frequency given (a) the research procedures that are described in the protocol-related documents, such as the Institutional Review Board (IRB)-approved research protocol and informed consent document; and (b) the characteristics of the participant population being studied;
- Related or possibly related to participation in the research ("possibly related" means there is a reasonable possibility that the incident, experience, or outcome may have been caused by the procedures involved in the research); and

```
Protocol 843748–
GET VIRTUAL PD
IMAGINE-PD
```

• Suggests that the research places participants or others at a greater risk of harm (including physical, psychological, economic, or social harm) than was previously known or recognized.

8.3.2 Unanticipated Problem Reporting

Unanticipated problems (UPs) such as:

- Complaint of a participant when the complaint indicates unexpected risks, or the complaint cannot be resolved by the research team
- Breach of confidentiality
- Incarceration of a participant when the research was not previously approved under Subpart C and the investigator believes it is in the best interest of the subject to remain on the study
- Premature closure of a study (e.g., due safety, lack of efficacy, feasibility, financial reasons, etc.)

should be reported by the investigator to the Institutional Review Board (IRB). The UP report will include the following information:

- Protocol identifying information: protocol title and number, PI's name, and the IRB project number;
- A detailed description of the event, incident, experience, or outcome;
- An explanation of the basis for determining that the event, incident, experience, or outcome represents an UP;
- A description of any changes to the protocol or other corrective actions that have been taken or are proposed in response to the UP.

To satisfy the requirement for prompt reporting, UPs will be reported using the following timeline:

- UPs that are serious adverse events (SAEs) will be reported as any other SAE.
- Any other UP will be reported to the IRB within 3 months of the investigator becoming aware of the problem.

All UPs should be reported to appropriate institutional officials (as required by an institution's written reporting procedures), the supporting agency head (or designee), and the Office for Human Research Protections (OHRP) within 3 months of the IRB's receipt of the report of the problem from the investigator.

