8.3.3 Reporting Unanticipated Problems To Participants

For all UPs participants will be informed via mailing at the end of the study. Any UP deemed study intervention related will be included in the informed consent for subsequent participants.

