10.1.1.2 Consent Procedures and Documentation

Informed consent is a process that is initiated prior to the individual's agreeing to participate in the study and continues throughout the individual's study participation. Consent forms will be Institutional Review Board (IRB)-approved and the participant will be asked to read and review the document. The investigator will explain the research study to the participant and answer any questions that may arise. A verbal explanation will be provided in terms suited to the participant's comprehension of the purposes, procedures, and potential risks of the study and of their rights as research participants. Participants will have the opportunity to carefully review the written consent form and ask questions prior to signing. The participants should have the opportunity to discuss the study with their family or surrogates or think about it prior to agreeing to participate. The participant will sign the informed consent document prior to any procedures

Page 34 of 41

being done specifically for the study. Participants must be informed that participation is voluntary and that they may withdraw from the study at any time, without prejudice. A copy of the informed consent document will be given to the participants for their records. The informed consent process will be conducted and documented in the source document (including the date), and the form signed, before the participant undergoes any study-specific procedures. The rights and welfare of the participants will be protected by emphasizing to them that the quality of their medical care will not be adversely affected if they decline to participate in this study.

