10.1.9 Protocol Deviations

A protocol deviation is any noncompliance with the clinical trial protocol, International Conference on Harmonisation Good Clinical Practice (ICH GCP), or protocol requirements. The noncompliance may be either on the part of the participant, the investigator, or the study site staff. As a result of deviations, corrective actions are to be developed by the site and implemented promptly.

These practices are consistent with ICH GCP:

Protocol 843748-
GET VIRTUAL PD
IMAGINE-PD

- 4.5 Compliance with Protocol, sections 4.5.1, 4.5.2, and 4.5.3
- 5.1 Quality Assurance and Quality Control, section 5.1.1
- 5.20 Noncompliance, sections 5.20.1, and 5.20.2.

It is the responsibility of the site investigator to use continuous vigilance to identify and report deviations within 10 working days of identification of the protocol deviation. All deviations must be addressed in study source documents, reported to IRB, per their policies. The site investigator is responsible for knowing and adhering to the reviewing IRB requirements.

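### Unanticipated problems that are not SAEs may take 3 months to reach the IRB, and enrolled participants are scheduled to hear of any unanticipated problem only by a mailing at the end of the study

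*Combined protocol and SAP*

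**What the plan says.** Section 8.3.1 defines a UP as an event that is unexpected, is at least possibly related to the research, and points to more risk of harm than was known before. Economic and social harm count. Section 8.3.2 gives four examples: certain participant complaints (including those that reveal unexpected risks), breach of confidentiality, incarceration of a participant, and premature closure of the study.

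The timeline in section 8.3.2 opens with the words "To satisfy the requirement for prompt reporting" and has two branches:

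- "UPs that are serious adverse events (SAEs) will be reported as any other SAE". Section 8.2.6 makes that route immediate: "The study clinician will immediately report to the IRB any serious adverse event".
- "Any other UP will be reported to the IRB within 3 months of the investigator becoming aware of the problem". Institutional officials, the supporting agency and OHRP follow within a further 3 months of the IRB's receipt.

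For participants, section 8.3.3 says: "For all UPs participants will be informed via mailing at the end of the study". Section 8.2.7 has the same rule for adverse events: "For all events, AE and SAE, participants will be informed via mailing at the end of the study". Both sections add that anything judged related to the study intervention goes into the consent form for people who enrol later.

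Three other sections bear on this. Under section 10.1.9 the investigator must "report deviations within 10 working days of identification of the protocol deviation". Section 10.1.2 requires the PI to inform participants, the IRB and the sponsor promptly if the study is suspended or stopped early. Section 10.1.1.2 describes consent as a process that "continues throughout the individual's study participation".

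**The concern.** A UP is by definition a signal of new risk, and this protocol's slow branch is the one that covers privacy events. Section 2.3.1 names genetic discrimination and re-identification among the risks of taking part, and section 10.1.3 states that an outside laboratory receives the name, date of birth and genetic status of those it tests. A participant who has consented but not yet received results has a real decision left to make: whether to go on to disclosure. Under the scheduled rules, that person need not hear of the new risk before making it. If the UP is judged intervention-related, someone who enrols later is told at consent while the person already enrolled waits for the mailing.

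**Working it through.** The plan has no computed figure to reproduce here. The check compares the reporting rules and then does simple timing arithmetic.

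**Rules side by side**

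| Event | Time to IRB | Scheduled notice to enrolled participants |
|---|---|---|
| UP that is an SAE (8.3.2, 8.2.6) | Immediate | Mailing at end of study (8.3.3, 8.2.7) |
| Any other UP (8.3.2) | Up to 3 months | Mailing at end of study (8.3.3) |
| Protocol deviation (10.1.9) | 10 working days to report; IRB reporting follows IRB policy | None stated |
| Premature termination or suspension (10.1.2) | Promptly | Promptly |

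Premature closure falls in both the second and the fourth rows, so one event carries two different standards.

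**Inputs.** Enrolment of 3 per week (5.4); N = 320 (1.1); study duration 36 months (1.1); Visit 2 disclosure at Day 28-56 and Visit 4 at Day 210-238 (12.1). I take 3 months as 13 weeks, or 91 days, and a month as 30.4 days.

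**Before the IRB must be told**

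- Entrants: 3 × 13 = 39, and 39 / 320 = 12.2%.
- With a 10-working-day limit (2 weeks): 3 × 2 = 6, and 6 / 320 = 1.9%.
- Disclosure at Day 28-56 comes 91 − 56 = 35 to 91 − 28 = 63 days before the 91-day limit for someone who consents on the day the UP becomes known.
- People already enrolled and awaiting disclosure at any time, in steady recruitment: 3 × 4 weeks = 12 to 3 × 8 weeks = 24. All would be due for disclosure inside the 91 days.

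These counts ignore attrition. They assume that recruitment runs at the planned rate, is not paused, and that the whole 3 months is used, so they are upper figures.

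**Wait for the mailing.** Section 4.3 defines only when a participant has completed, so the end of the study has two possible meanings.

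- Month 36 of the trial, for a participant enrolled at month 0: the last visit is at 210 / 30.4 = 6.9 to 238 / 30.4 = 7.8 months. The wait after it is 36 − 7.8 = 28.2 to 36 − 6.9 = 29.1 months.
- The participant's own end: no further wait, but counselling, testing and disclosure are already over.

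**The case against.** Much can be said for the plan. The 3-month limit is a maximum, and staff may act sooner. Events that threaten life or health go to the IRB immediately. Section 8.3.2 requires the UP report to describe corrective actions taken or proposed, and section 10.1.2 allows suspension for unexpected risk, with notice to participants. The person who complains or is incarcerated already knows of the event. The 10-working-day comparator is also looser than it looks: section 10.1.9 ties IRB reporting to the IRB's own policies, which are not in the documents and may be stricter.

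All of that stands, but none of it obliges anyone to tell enrolled participants about a UP before the end of the study unless the study is suspended or stopped.

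Several stronger readings are tempting, and the documents do not support them:

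- A reader might infer that every UP can wait 3 months. UPs that are SAEs cannot, and SAEs are not lesser matters than other UPs.
- A reader might infer that a breach which is also a deviation has conflicting deadlines. Both are upper limits, and meeting the shorter one meets both.
- A reader might infer that section 8.3.3 contradicts section 10.1.1.2. Both can be followed; what is missing is a step that delivers new risk information during participation.
- A reader might infer that new enrollees always learn first. That holds only for UPs judged related to the intervention. A confidentiality breach may not qualify, and then no participant has earlier notice.
- A reader might double the entrant count to 3 × 26 = 78 by running on to the OHRP limit. That clock starts when the IRB has the report and does not govern enrolment or participant notice.

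**Conclusion.** The point holds. For UPs that are not SAEs, a 3-month allowance to the IRB sits badly with the stated aim of prompt reporting and with the protocol's own 10 working days for deviations. For all UPs, the only scheduled notice to people already enrolled is the end-of-study mailing. Premature closure is treated differently in sections 8.3.2-8.3.3 and in section 10.1.2, and these must be reconciled.

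The size is up to about 39 entrants (12% of 320) before the IRB must know, on the assumptions stated with the arithmetic. About 12 to 24 people already enrolled could also pass disclosure uninformed in that time. The wait of about 28 months after the last visit depends on the end of the study meaning month 36 and on enrolment at month 0. It applies to someone who has finished, so it measures late notice and not continued exposure. On the other reading of the term, notice still comes after every decision it could have informed.

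This is a participant-protection and drafting matter with no bearing on sample size or analysis. No outside regulatory time limit is relied on, because the documents give none. The change should be made, but it does not call the design into question.

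**What to change.** - **Section 8.3.2:** shorten the IRB limit for UPs that are not SAEs to no more than the 10 working days used in section 10.1.9, or the reviewing IRB's limit if that is shorter. The 10 days are borrowed from the protocol's deviation rule; the documents fix no correct figure for UPs.
- **Sections 8.3.2 and 8.3.3:** reconcile premature closure with section 10.1.2.
- **Sections 8.2.7 and 8.3.3:** add that affected participants are told once the IRB has agreed the wording. Add that any new risk put into the consent form is also sent, before their next visit, to participants still in the study. Keep the end-of-study mailing as a summary, and say what the end of the study means.

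The cost is a wording amendment and occasional IRB-approved letters. In steady recruitment a notice to everyone still in the study would reach at most about 3 × 30 = 90 to 3 × 34 = 102 people (Day 210-238 is 30 to 34 weeks). No visits, data or analyses change.
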